## 2.2 Secondary Objectives

- **2.2.1** To evaluate the overall survival (OS), which is defined as the time between date of registration and the date of death due to any cause. In analyzing the OS, it is important to take into account the MSKCC prognostic criteria defined by Motzer et. al. mRCC patients and compare the outcome in the appropriate risk categories [90].
- **2.2.2** To evaluate progression free survival (PFS), which is defined as the time between date of registration and the first date of documented disease progression or date of death due to any cause.
- **2.2.3** To evaluate time to progression (TTP), which is defined as time between date of registration and date of documented progression.
- **2.2.4** To evaluate the local control rate of irradiated lesions.
- **2.2.5** To evaluate median response duration, which is defined as the time between the date a response (CR or PR) was first seen until date of progression.
- **2.2.6** To measure treatment-related tumor-specific immune response.
- **2.2.7** To evaluate the tolerability and toxicity of this regiment as measured according to CTCAE v4.0.
- **2.2.8** To measure the improvement in health-related quality of life (HRQoL).

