## 2.4 Endpoints

- **2.4.1 Response:** Treatment response will be measured using the immune related RECIST criteria (iRECIST) which are a minor modification of RECIST 1.1 for immunotherapy [91].
- **2.4.2 Death:** Death due to any cause, although in mRCC patient population, the overwhelming majority is expected to be secondary to disease progression.
- **2.4.3 Progression:** Progression will be defined according to the iRECIST criteria and verified by a second set of imaging at least 6 weeks apart.
- **2.4.4 Immune Response:** Immune response will be measured using ELISpot assay, T-cell proliferation assay and ELISA.
- 2.4.5 Toxicity: Toxicity will be measured using CTAE v4.0
- **2.4.6 HRQoL**: HRQoL will be measured using FACT-G, EQ-5D and FKSI questionnaire at baseline, after HD IL-2, and at four-month intervals after treatment.
- 2.4.7 **Cost-effectiveness analysis**: Health care utilization data needed to assess costs will be obtained from treatment records to include costs of hospitalization, treatment, ER visits, physician and clinic visits and medications. Markov modeling with probabilistic sensitivity analysis will be used to correlate quality-adjusted survival and cost.

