## 6.0 Measurement of Effect

## 6.1 Antitumor Effect

For the primary endpoint, response and progression will be evaluated in this study using the new international criteria proposed by the Response Evaluation Criteria in Solid Tumors (RECIST) Committee [JNCI 92(3):205-216, 2000], which was also used by the two randomized trials of HD IL-2 being used as historic controls for this trial [35, 36]. The only change from RECIST v.1.1 being implemented in this study is a confirmation of new lesions or progressive disease (PD) by a second scan >6wks apart, based on the immune RECIST (irRC) criteria proposed by Wolchok. et. al that is appropriate for immune-related treatment response [91]. This is primarily because immune response often can take longer time as compared to chemotherapy before producing a radiographic response and during this time new lesions may arise which will eventually regress and if it were not for a second confirmation, these patients would be labeled to have failed therapy. In addition, the majority of mRCC responders to HD IL-2 usually produce a durable response (median response duration of 24 months), therefore, this change will not affect the outcome [35]. Additional criteria for bone lesions and clinical endpoints of pathologic fracture and cord compression are added to this study (see Section 6.1.4).

Changes in only the largest diameter (unidimensional measurement) of the tumor lesions are used in the RECIST v1.1 criteria outlined in http://www.recist.com/.

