#### 6.1.4 Response Criteria

#### 6.1.4.1 Evaluation of Target Lesions

Complete Response (CR): Disappearance of all target lesions, determined by two separate observations conducted not less than 4 weeks apart. There can be no appearance of new lesions.

Partial Response (PR): At least a 30% decrease in the sum of the longest diameter (LD) of target lesions, taking as reference the baseline sum LD. There can be no appearance of new lesions.

Progressive Disease (PD): At least a 20% increase in the sum of the LD of target lesions, taking as reference the smallest sum LD recorded since the treatment started, or the appearance of one or more new lesions verified by a second scan > 6 weeks apart.

Stable Disease (SD): Neither sufficient shrinkage to qualify for PR nor sufficient increase to qualify for PD, taking as reference the smallest sum LD since the treatment started.

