# 11.3 Data Analyses Plans

This is a single-arm Phase II trial of SABR and HD IL-2 for mRCC patients. PFS and OS, will be estimated using the Kaplan-Meier approach along with the 95% confidence interval. Exact binomial method will be used to calculate the response rate, toxicity and the corresponding 95% confidence interval. One-sample log-rank test [121] will be used to test if the survival endpoints such as OS or PFS are significantly different from those in the historical control reported in McDermott et. al [35].

Generalized estimating equation (GEE) analysis will be conducted to test if the median number of spots in Elispot of the PBMC collected from patients are significantly different over time (before starting of treatment and after SBRT, at 8 weeks and six months). T-Cell proliferation SI will also be evaluated in the same manner.

HRQol, CEA and quality adjusted survival time analysis is described in Section 10.

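### The PFS test against the historical HD IL-2 arm compares progression confirmed on a second scan with progression scored by RECIST, and the plan does not clearly say which scan dates the event

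*Combined protocol and SAP*

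**What the plan says.** Section 11.3 names the method for the historical comparison: a one-sample log-rank test, to be "used to test if the survival endpoints such as OS or PFS are significantly different from those in the historical control", namely the HD IL-2 results in reference 35. It gives no alpha, sidedness, power or reference curve for this test.

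Section 6.1 describes how progression is scored. It adopts RECIST, "which was also used by the two randomized trials of HD IL-2 being used as historic controls for this trial", and gives as the sole departure a "confirmation of new lesions or progressive disease (PD) by a second scan >6wks apart". Section 2.4.3 builds the same requirement into the progression endpoint, which must be "verified by a second set of imaging at least 6 weeks apart". Section 6.1.4.1 repeats it less clearly: in the PD definition, "the appearance of one or more new lesions verified by a second scan > 6 weeks apart" may or may not also govern the 20% growth criterion.

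Section 2.2.2 defines PFS as "the time between date of registration and the first date of documented disease progression or date of death due to any cause", and section 6.1.7 is similar. Neither says whether the first or the confirming scan supplies the date. Sections 6.1.4.5 and 6.1.4.6 add pathologic fracture at an untreated site and cord or cauda equina compression as progression events. No PFS analysis under unconfirmed RECIST is planned.

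**The concern.** A one-sample log-rank test takes its expected events from the reference curve, so an event must mean the same thing in both series. On the protocol's own account it does not. The reference arm was scored by RECIST. Here a first progression counts only if a later scan verifies it. A patient whose first progression is not verified stays event-free longer than the same patient would under the reference rule. If the confirming scan also supplies the date, every scan-detected progression moves later by at least 6 weeks.

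Section 6.1 argues that the change is harmless because responses to HD IL-2 last. That argument is about responders. At the 23% null response rate of section 11.2, about 77% of patients do not respond, and their progression dates are the ones most exposed to the rule.

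At stake is a secondary comparison. Section 1.4 nevertheless lists PFS among the endpoints that could each help to justify a phase III trial.

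**Working it through.** **The plan's own figures.** None is given for the PFS test. The response design in section 11.2 reproduces: 3/17 then 9/33 gives early termination 0.427, expected size 17 + 16 × (1 − 0.427) ≈ 26.2, alpha 0.197 and power 0.805. I take n = 33 from there.

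**Inputs.** From the documents: n = 33, a confirming interval of at least 6 weeks, and scans every 8 weeks for the first eight months (section 4.4). Assumed, because the documents are silent: exponential historical PFS with median m of 3 to 12 months, a two-sided 5% test, and 24 to 48 months of follow-up per patient. There is no treatment effect throughout. The statistic is Z = (O − E)/√E.

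**Closed form, event dated at the confirming scan.** With hazard λ = ln 2/m and delay d, and ignoring censoring, each patient contributes one observed and on average 1 + λd expected events, so O/E = 1/(1 + λd).

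- m = 3, d = 6 weeks (1.38 months): λd = 0.231 × 1.38 = 0.319, O/E = 0.758, E = 33 × 1.319 = 43.5, Z ≈ (33 − 43.5)/√43.5 = −1.59.
- m = 12, d = 6 weeks: λd = 0.0578 × 1.38 = 0.080, O/E = 0.926, E = 35.6, Z ≈ −0.44.
- m = 3, d = 8 weeks (1.84 months): λd = 0.425, O/E = 0.702, E = 47.0, Z ≈ −2.04.

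Simulated O/E for the three cases is 0.758, 0.914 and 0.702. Censoring explains the small gap at m = 12.

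**Closed form, event backdated to the first scan.** If a share u of first progressions is never verified and those patients truly progress a mean of 6 months later, O/E = 1/(1 + 6λu). At m = 3 this is 1.000, 0.878 and 0.783 for u = 0, 10% and 20%; simulation gives 1.001, 0.878 and 0.784.

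**Simulated rejection in favour of the regimen** (40,000 trials per setting, fixed delay, no scan calendar):

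| Scoring in this trial | m = 3 | m = 4 | m = 6 | m = 9 | m = 12 |
|---|---|---|---|---|---|
| Same as reference | 1.6% | 1.8% | 1.8% | 1.8% | 1.8% |
| Backdated, 10% unverified | 10.1% | not run | 4.4% | 3.3% | 2.9% |
| Backdated, 20% unverified | 26.8% | not run | 9.0% | 5.6% | 4.4% |
| Dated 6 weeks later | 29.5% | 17.0% | 8.9% | 5.8% | 4.6% |
| Dated 8 weeks later | 52.6% | 30.2% | 14.0% | 8.3% | 6.1% |

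If 10% of first events are deaths, which need no confirmation, the 6-week row runs from 24.4% (m = 3) to 4.2% (m = 12). With n = 38, the maximum shown in the study summary, it runs from 35.6% to 5.0%.

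**With progression found only at scheduled scans**, the ranges for medians of 12 down to 3 months are:

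- matched scoring: about 1.5–1.8%
- backdated, 10% unverified: about 3–9%
- backdated, 20% unverified: about 4–23%
- dated exactly 6 weeks later: about 4–19%
- dated at the next scheduled scan: about 7–52%

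I use these as the headline figures because they follow the trial's scan calendar. The table shows how much they depend on the model.

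**The case against.** Several points on the other side stand.

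- **Dating.** A reader might infer that PFS is dated at the confirming scan, which gives the largest figures. The documents do not say so. The section 2.2.2 wording leans towards the first scan, and section 6.1.6 is similar for response duration. Under backdating, the bias comes only from first progressions that are never verified, and the documents give no rate for those.
- **Direction.** A reader might infer that the scoring difference must favour the regimen. It need not. The fracture and cord-compression events of sections 6.1.4.5 and 6.1.4.6 are additions that can only shorten PFS. Section 6.1.2 also removes SABR-treated lesions from the target sum, with unknown net effect.
- **Scope.** Confirmation is uneven. Section 6.1.4.2 does not ask for it for non-target progression, and section 6.1.4.1 ties it most closely to new lesions. The calculations apply it to all scan-detected progression, the widest reading.
- **The control.** That the reference arm used unconfirmed progression is inferred from section 6.1's account of what this trial changed. The cited trial could not be checked.
- **Response rate.** A reader might infer that the primary comparison with 23% is inflated in the same way. The documents do not support that: section 6.1.4.1 bars any new lesion for CR and PR, and they give no basis for a shifted null rate.
- **Weight.** PFS is secondary, and the only formal go rule is more than 9 responses in 33.

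None of this removes the mismatch. Section 6.1's durability argument concerns response, and the confirmation rule exists because some early progressions are expected to regress.

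**Conclusion.** The concern holds in a limited form. The planned PFS test sets a confirmed endpoint against one scored by RECIST, and the confirmation rule can by itself lengthen PFS relative to the reference curve.

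The size depends on two things the documents omit: the historical PFS curve and the dating rule. Under backdating, the more natural reading, the effect runs from nil when all first progressions are verified to the 4–23% range when 20% are not. Under confirming-scan dating it is material at medians of 3 to 6 months and small near 12 months for a 6-week delay. The added clinical events push the other way by an amount nobody can state from the documents, so the net bias is uncertain. OS is unaffected, and the response-rate decision does not depend on this test. It is a moderate point on a secondary analysis, worth making because the repair is cheap.

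**What to change.** In section 11.3:

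1. For the comparison with the historical control, define the PFS event as the first scan meeting RECIST progression without confirmation, or death. Leave out the study-specific fracture and cord-compression events unless they also meet RECIST progression.
2. Report confirmed PFS descriptively by Kaplan-Meier, and state whether the first or the confirming scan dates it.
3. Note that SABR-treated lesions are outside the target sum, a difference from the historical arm that this rescoring does not remove.

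In section 6.1, limit the assurance that confirmation makes no difference so that it refers to response only.

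The cost is SAP wording and one derived date per patient from scans already taken. The PFS comparison may look slightly less favourable. Treatment, visits and sample size do not change.

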#### 4.4 Duration of Follow Up

Subjects will be followed for ten years or death (although findings will be analyzed and reported at a median follow up of 2-4 years), whichever occurs first. Subjects removed from treatment for unacceptable adverse events will be followed until resolution or stabilization of the adverse event. The follow-up will be every 8 weeks (+/- 2 Weeks) from study registration with imaging studies and physical exam every 8 weeks for the first eight months, then every 12 weeks (+/- 2 Weeks) until two years, then every four months thereafter for a total of five years, and then every six months (+/- 1 month) for a total of ten years. See section 5.0 for detail.

Subjects who show progressive disease will be followed for survival and will no longer strictly adhere to study calendar. QOL questionnaires will be completed every 4 months until 1 year after treatment.

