# 6.3 Quality of Life (QoL)

#### 6.3.1 Functional Assessment of Cancer Therapy-P (FACT-G) and Kidney Symptom Index (FKSI)

Patient-reported functional status will be assessed with prostate cancer subscales of the Functional Assessment of Cancer Therapy-General (FACT-G) (See appendix for form). The FACT-G is a 28-item questionnaire that uses 5-point Likert-type response choices (0 = not at all; 1 = a little bit; 2 =somewhat; 3 = quite a bit; 4 = very much). It will take less than 10 minutes to complete the questionnaire. The Trial Outcome Indices (TOI) also will be utilized to measure the summed functional well-being, physical well-being [103, 104]. A 5-point deterioration in the FACT-G TOI between pre-treatment and at post treatment or at year 1 will be considered clinically significant [105].

The FACT-G and FKSI will be given on Day 1 and 28 similar to several other quality of life studies [106],[82], [85]

The FKSI is a 15 question validated symptom index for kidney cancer patients which has been used in several metastatic renal cell cancer studies [106]. This scale focuses on symptoms predominantly related to kidney cancer such as energy, fatigue, pain, bone

pain, weight loss, shortness of breath, cough, fever, hematuria. This subscale of the FKSI-DRS was validated in another study as well [107]

The first analysis of change in QOL from baseline to 8 weeks will only be performed on patients who are still alive at 8 weeks. Changes in QOL will be also analyzed using all available data at baseline, 8, 16, 24, and 36 weeks with semiparametric generalized estimating equations (GEE).

Additionally, similarly we will also compare the percentage of patients with an effect size for the change in FKSI (FKSI) scores between pre-treatment and post treatment which will allow us to compare the percentage of patients whose functional status remains more similar to baseline levels.

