#### 11.2 Sample Size and Accrual

The previous studies show that the maximum RR for mRCC patients treated with HD IL-2 is 23% [35]. We expect a >60% improvement in this rate leading to a 36.8% RR for mRCC patients when treated with SABR and IL2. The calculation of the sample size is based on the RR and Simon's optimal two-stage design will be used with  $(\alpha,\beta)=(0.20, 0.20)$  [120]. The RR of 23% is set as the lowest desirable rate and 36.8% is the rate we are targeting. We chose type I error of 0.20 and type II error of 0.20. That is, if the true response rate is less than 23%, the probability of wrongly accepting the treatment for further study is 20%, and if the true response rate exceeds 36.8%, the probability of wrongly rejecting it for further study is 20%. According to the optimal two-stage design, a maximum of 33 patients will be needed. In the first stage, 17 patients will be evaluated. If 3 or fewer responses are observed, then the trial will be terminated for futility. Otherwise an additional 16 patients (second stage) will enter the trial. Finally, if more than 9 responses are observed among 33 patients, then the regimen

(SABR+IL-2) may be considered as the experimental arm of a Phase III trial. The average sample size for this phase II trial is 26.2 patients, and the probability of early termination is 0.43 for a drug with response probability of 23%.

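### The GEE test of change in ELISpot and T-cell proliferation has no small-sample correction: at the usual default it would err about 9% (33 patients) to 14% (17 patients) at an assumed 5% level

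*Combined protocol and SAP*

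**What the plan says.** Section 11.3 commits to a formal test: "Generalized estimating equation (GEE) analysis will be conducted to test if the median number of spots in Elispot of the PBMC" collected from patients differs significantly over time. The visits are "before starting of treatment and after SBRT, at 8 weeks and six months", so there are four. It adds: "T-Cell proliferation SI will also be evaluated in the same manner". Immune response is a secondary objective (2.2.6).

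Section 6.3.1 also uses GEE, described as semiparametric, for quality of life: "Changes in QOL will be also analyzed using all available data at baseline, 8, 16, 24, and 36 weeks". That is five visits. Sections 1.6 and 10.1 describe the quality-of-life work as descriptive.

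The number of patients comes from the primary-endpoint design in section 11.2: "a maximum of 33 patients will be needed. In the first stage, 17 patients will be evaluated". The Study Summary gives a different maximum, 38.

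For the GEE analyses the documents name no variance estimator, working correlation, link, reference distribution, coding of time, significance level or small-sample correction. The only stated type I error is 0.20, for the response-rate design. Section 11.3 uses 95% intervals for its other analyses.

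**The concern.** GEE inference normally rests on the sandwich covariance with a chi-square or z reference. Both are justified only as the number of independent clusters grows. With a few dozen patients two things go wrong. The sandwich is built from fitted residuals and is too small on average. The chi-square reference also ignores the fact that the covariance was itself estimated. Both errors make the test reject too often, and the effect grows with the number of time contrasts tested together.

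What is at stake is the immune-response finding. The clinical rationale in section 1.4 says that each secondary outcome, tumor-specific immune response among them, could be used to justify a phase III trial. A claim of significant immune change should carry the error rate that it states.

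**Working it through.** **Inputs.** Number of patients n: 17 (stage 1 only) or 33 (section 11.2), with 38 from the Study Summary and 26 as the rounded expected sample size. Contrasts tested jointly, q: 3 for four visits (section 11.3), 4 for five visits (section 6.3.1), taking time as categorical. Nominal level: 5%, assumed.

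**The plan's own figures.** Under the design in section 11.2 (stop at 3 or fewer responses of 17; positive if more than 9 of 33), at a response rate of 23%:
- Probability of stopping early: P(X ≤ 3 | 17, 0.23) = 0.427.
- Expected sample size: 17 + 16 × (1 − 0.427) = 26.2.
- Type I error: 0.197.

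At 36.8% the probability of stopping is 0.078 and the power 0.805. The stated 0.43 and 26.2 reproduce. So n = 17 has probability 0.43 at a 23% response rate and 0.08 at 36.8%.

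**Size of the default test.** With complete data and categorical time, the uncorrected sandwich Wald statistic W equals n/(n − 1) times Hotelling's T². Because T² = [(n − 1)q/(n − q)] F(q, n − q), it follows for normal data that

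W = [nq/(n − q)] F(q, n − q), and true size = P{ F(q, n − q) > c (n − q)/(nq) },

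where c is the 95% point of chi-square on q degrees of freedom. For n = 33 and q = 3, c = 7.815, the cut-off is 7.815 × 30/99 = 2.368, and P{F(3, 30) > 2.368} = 0.090. For n = 17 the cut-off is 7.815 × 14/51 = 2.145, and P{F(3, 14) > 2.145} = 0.140.

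| n | 1 contrast | 4 visits (q = 3) | 5 visits (q = 4) |
|---|---|---|---|
| 17 | 7.5% | 14.0% | 18.6% |
| 26 | 6.6% | 10.4% | 12.9% |
| 33 | 6.3% | 9.0% | 10.9% |
| 38 | 6.1% | 8.4% | 9.9% |

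**Check by simulation.** GEE in statsmodels (Gaussian, exchangeable, default robust covariance; 1,200 runs per setting) gave 13.4% and 8.8% for four visits at n = 17 and 33, and 17.9% and 10.8% for five. A linear trend over four visits gave 8.0% and 6.2%.

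**Intervals for one contrast.** The default width relative to the correct one is 1.960 × √((n − 1)/n) / t(0.975, n − 1). At n = 33 this is 1.960 × 0.985/2.037 = 0.948. At n = 17 it is 1.960 × 0.970/2.120 = 0.897. The intervals are about 5% and 10% too narrow.

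**Departures from complete normal data.** With an assumed 20% loss per visit, the simulated size for four visits reached 18% at n = 17 and 11% at n = 33; for five visits, 27% and 16%. For overdispersed counts with a log link (Poisson GEE, no missing data), four visits gave 29% and 19%, and five gave 40% and 22%. These are illustrations: the plan states neither a loss rate nor a link.

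**The case against.** The strongest reply is that the plan does not say how the GEE will be run. A reader might infer that section 11.3 prescribes large-sample robust standard errors. It does not; it is silent. The 5% level and categorical time are likewise assumptions. This stands, and the error rates are therefore conditional. It does not remove the point, because running the named method at its usual default gives those rates. A test across four listed visits, with no trend mentioned, also reads most naturally as categorical.

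A reader might take the 18.6% figure as the error of the immune tests. It belongs to the five-visit quality-of-life model at n = 17. That sample size arises only after a futility stop, and sections 1.6 and 10.1 call quality of life descriptive.

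A reader might also infer that confidence intervals mislead as badly as the overall test. They do not: intervals concern single contrasts, where the error is about 6-8%.

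Finally, section 4.4 says: "Subjects who show progressive disease will be followed for survival and will no longer strictly adhere to study calendar". It is tempting to conclude that informative dropout materially biases the GEE. The next sentence of 4.4 keeps quality-of-life questionnaires going every four months to one year, and section 9.0 makes the blood samples mandatory. Some six-month samples may well be lost after progression, but the documents give no rate. Even an assumed 40-60% dropout produced a false rise of only 0.05-0.09 SD in simulation. That is not enough to support a claim of material bias.

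**Conclusion.** The point holds for the ELISpot and SI tests in section 11.3. Under an uncorrected sandwich, a chi-square reference, categorical time and an assumed 5% level, the overall test has a true error of about 9% at 33 patients and 14% at 17 with complete normal data. It is higher with missing samples or overdispersed counts under a log link. If only a trend or a single contrast is tested, the error is about 6-8%.

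For quality of life the corresponding overall figure is 11-19%, and it matters only if a test is reported. The go/no-go rule in section 11.2 uses response counts and is untouched. The calculation concerns means; that section 11.3 speaks of a median is a separate question.

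**What to change.** In section 11.3, and in 6.3.1 if any quality-of-life p-values or intervals are reported, state that:
- time is categorical, and the significance level is given;
- the covariance is a bias-corrected sandwich (for example Mancl-DeRouen);
- joint tests use an F reference on (q, n − q) degrees of freedom, and single contrasts a t reference on about n − 1.

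The scaling should be written down. With complete data, Mancl-DeRouen multiplies the covariance by (n/(n − 1))². The statistic W* (n − q)/((n − 1)q), with W* the corrected Wald statistic, is then (n − 1)/n times an F(q, n − q) variable. For q = 3 its size is P{F(q, n − q) > F(0.95) × n/(n − 1)}: 4.5% at n = 33 and 4.2% at n = 17. In simulation, bias correction with an F reference gave 2.9-7.0% over n = 17, 26 and 33, including skewed data and dropout. Bias correction with the chi-square reference kept is not enough: 7-19%.

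A linear mixed model with Kenward-Roger degrees of freedom is an optional alternative. It is not needed to cure this error, and moving to a log scale would change what is estimated.

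The cost is SAP wording, larger p-values and somewhat wider intervals. For one contrast with complete data the interval widens by (33/32) × (2.037/1.960) = 1.07 at n = 33 and (17/16) × (2.120/1.960) = 1.15 at n = 17.

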# 9.2 Assay Methodology

- 9.2.1 Elispot: IFN-γ ELISpot assays will be performed according to manufacturer's protocol using a commercial ELISpot kit (MabTECH). Briefly, 96 well plates are coated overnight with 0.015 mg/ml of an anti-human IFN-g monoclonal antibody. PBMC from patients will be incubated in triplicates wells and stimulated in the presence of either PA2024 (10µg/ml), protein lysate from patient biopsy (50µg/ml) or 5 ng/ml PMA and 0.5 ng/ml ionomycin as positive control and albumin as negative control. For ELISPOT assays, plates are incubated for 48 hours, washed, probed with biotinylated anti-IFNg, further washed, and then incubated with streptavidin alkaline phosphatase. Spot development is achieved with 5-bromo-4-chloro-3-indolyl phosphate/nitroblue tetrazolium (BCIP/NBT; Invitrogen) and spots are enumerated by an automatic ELISpot reader.
- **9.2.2 ELISA**: In this procedure, patient tumor tissue lysate is first adsorbed to an EIA 96 well microplate (Fischer). Patient plasma is then added to each well as a source of primary antibody and serially diluted. After extensive washes, detection enzyme (HRP)-linked anti-human mAb is then added to each well and allowed to bind. Appropriate substrate is then added to each well and color development occurs within 5-60 min. UV Microplate Reader will be used to read the plates
- 9.2.3 H-thymidine Proliferation Assay: PBMC from patients will be incubated in a similar manner as above for five days at 37 °C then overnight with 0.5 mCi tritiated H-thymidine, harvested onto a glass-fiber filter using a 96-well FilterMate cell harvester. The radioactivity of the H-thymidine is detected by a direct betaplate counter. The degree of antigen-specific clonal T cell expansion will be expressed as a stimulation index (SI) of the ratio of H-thymidine incorporation by cells incubated with patient tumor lysate compared with media controls. An alternate method utilizing FACS analysis with carboxy fluorescein diacetate succinimidyl ester (CFSE) is also available [108].

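### Section 11.3 assigns GEE to test a change in the median ELISpot count, but standard GEE tests the mean, and no transformation, link or quantile version is given to close the gap

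*Combined protocol and SAP*

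**What the plan says.** Secondary objective 2.2.6 reads "To measure treatment-related tumor-specific immune response". Section 2.4.4 measures it by ELISpot, T-cell proliferation and ELISA.

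Section 11.3 gives the only stated analysis: "Generalized estimating equation (GEE) analysis will be conducted to test if the median number of spots in Elispot" differs over four occasions ("before starting of treatment and after SBRT, at 8 weeks and six months"). It adds: "T-Cell proliferation SI will also be evaluated in the same manner". Section 9.2.3 defines that index as a ratio.

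The outcome is a count. In section 9.2.1, "spots are enumerated by an automatic ELISpot reader" after incubation in triplicate wells, and no rule is given for combining the three wells. For ELISpot the documents state no transformation, link, working correlation, contrast, significance level, variance or power. The only rule for logarithmic analysis, including how to treat zeros, is for cytokines in section 9.2.7.

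**The concern.** GEE in its usual form estimates how the marginal mean depends on covariates, here time. For skewed counts the mean and the median are different quantities. They can also change differently if treatment alters the spread of the counts as well as their location. A few strong immune responders would produce that pattern: the mean rises while the typical patient does not change.

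The result could then be read as a shift in the median that did not occur. Section 1.4 (clinical rationale) names tumor-specific immune response among the outcomes that could help justify a phase III trial, so a misdescribed result has some consequence. A second risk is that analysis on the raw scale loses power if the counts are strongly skewed.

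**Working it through.** **Plan's own figure.** The only sample-size calculation is for response rate (section 11.2): "a maximum of 33 patients will be needed", with 17 in stage 1. At a true rate of 0.23, P(3 or fewer of 17) = 0.427 and expected N = 17 + 16 × (1 − 0.427) = 26.2. The full rule has attained alpha 0.197, and power 0.805 at a rate of 0.368. It reproduces, but it fixes only the patient numbers (17 and 33) used below and says nothing about ELISpot.

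**Assumed, because the documents give no values:** Poisson counts around log-normal patient levels, a median of 20 spots, complete data, two-sided 0.05.

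**Do the mean and median hypotheses diverge?** For a log-normal variable, mean = median × exp(s²/2), where s is the log-scale SD. With equal medians and s moving from s0 to s1, the ratio of means is exp((s1² − s0²)/2):
- 0.5 to 1.0: exp(0.375) = 1.45
- 0.5 to 1.3: exp(0.72) = 2.05

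With two occasions, identity-link GEE on raw counts reduces to a test of the mean paired difference. Simulated rejection rates at n=33, with equal medians:

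| Within-patient correlation (log scale) | Reference | Raw, s1=1.0 | Raw, s1=1.3 | log(count+1) |
|---|---|---|---|---|
| 0 | t | 18% | 31% | 5–6% |
| 0.5 | t | 26% | 40% | 5% |
| 0.5 | uncorrected robust z | 32% | 47% | 6–7% |

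The first row uses 4,000 data sets and the others 20,000. At n=17 with zero correlation the raw-scale rates are 8% and 10%. The raw test is right that the means differ; the error lies in calling the result a change in the median.

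**Power.** Four occasions; all post-baseline medians 1.6 times baseline; joint 3-df test of time with an F-type small-sample correction; 4,000 data sets per cell (Friedman 1,000):

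| n | Log-SD between / within patients | Raw, identity link | log(count+1) | Friedman |
|---|---|---|---|---|
| 33 | 0.3 / 0.3 | 1.00 | 1.00 | 1.00 |
| 33 | 0.8 / 0.5 | 0.75 | 0.92 | 0.89 |
| 33 | 1.2 / 0.8 | 0.25 | 0.57 | 0.49 |
| 17 | 0.3 / 0.3 | 0.93 | 0.93 | 0.91 |
| 17 | 0.8 / 0.5 | 0.40 | 0.59 | 0.56 |
| 17 | 1.2 / 0.8 | 0.10 | 0.26 | 0.24 |

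The loss at n=33, raw against log, is 0, 17 and 32 points.

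**Other choices the text leaves open.** A log link on raw counts fails differently. With no time effect, it rejects 6%, 12% and 25% of the time at n=33 across the three spreads, even with the F correction. On log(count+1), the uncorrected robust Wald test rejects 13–15% under the null at n=17 and 6.5–8.7% at n=33. The F correction brings this to about 5%.

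**The case against.** The strongest reply is that the sentence is incomplete rather than wrong. Nothing in section 11.3 says raw counts will be modelled. GEE can be fitted to log counts, and if those are symmetric it targets the median. This stands in part: GEE need not be abandoned. But the section states a median hypothesis and supplies nothing that would make the named method test it.

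A second reply is that median may mean the median of a sample's triplicate wells, which GEE can properly analyse as an outcome. The wording allows this. No well-summary rule confirms it, however, and the one such rule in section 9.2, for cytokines, takes a mean. Even on this reading the scale, link and handling of zeros stay open.

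A reader might infer that power is certainly lost. The documents do not support that: they give no ELISpot spread, and under mild skew the loss is nil.

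A reader might also take a large mean-to-median ratio at one time point as proof of a wrong test over time. It is not. If treatment only rescales a fixed distribution, the mean and median nulls coincide. They part only when shape or spread changes.

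Finally, this is one secondary endpoint, with no significance level or decision rule attached. That is correct and limits the weight of the point.

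**Conclusion.** The concern holds in a bounded form. As written, the analysis for objective 2.2.6 does not test the hypothesis stated for it, and the gap can change the conclusion as well as the label.

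If the median is unchanged and the log-scale SD rises from 0.5 to 1.0–1.3, a raw-scale analysis of 33 patients rejects about 18–47% of the time. The exact rate depends on the within-patient correlation and on whether a small-sample reference is used. The log-scale rate is about 5–6% with a t reference. The possible power loss runs from 0 to about 32 points at n=33. Every figure rests on assumed log-normal Poisson counts with a median of 20.

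The documents do not show that the sponsor will use raw counts, that ELISpot counts here will be strongly skewed, or that power will in fact be lost. The response-rate decision rule in section 11.2 is untouched.

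**What to change.** In section 11.3:
- Fit the GEE to log(spots+1) and log(SI) across the four listed occasions. Name the link, the working correlation and a small-sample correction.
- Report geometric-mean ratios to baseline with 95% CI, and drop the word median.
- State how the triplicate wells are summarised, and whether median was meant in that sense.
- If the population median itself is wanted, name a quantile method. A Wilcoxon signed-rank test would not serve, because it tests whether paired differences are symmetric about zero, not whether marginal medians are equal.

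The cost is a few sentences, with no change to patients, samples or assays. There is a small downside: the estimand becomes a geometric-mean ratio, which equals a ratio of medians only if the log values are symmetric, and the added constant matters at low counts. A sensitivity analysis with a different constant would show whether it does.
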